10.8 TRIAL SUBJECT EXIT

Trial Subjects exit the trial when no additional follow-up visits, procedures, or data collection are required. A subject is exited from the trial in the following instances:

- Subject fails enrollment criteria after written consent
- Subject is considered enrolled as "intent to treat" however surgeon is unable to complete the implant procedure*
- Subject has trial device explanted*
- Subject is lost-to-follow-up
- Subject withdraws from the trial
- Subject death
- Subject completes trial follow-up

* Subjects will be followed for 30 days or until any adverse events experienced by this cohort are resolved and then will be exited from the trial.

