9.2 ANALYSIS POPULATION

The analyses of safety data will include all enrolled subjects. Subjects are considered enrolled in the clinical trial after meeting the enrollment criteria, signing the informed consent and the surgeon determines that the index valve can be implanted.

The analyses of performance data will include the index valve population, defined as all subjects that are enrolled into the trial and that are implanted with the index valve.

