10.2.3 IMPLANT ASSESSMENT

A Transesophageal echo (TEE) should be performed within 1 hour after the index valve is implanted (from cross clamp removal) to assess placement and index valve function. The echo requirements are in the Echo Manual.

Procedural information, findings, results and device identification information to be recorded is identified in Error! Reference source not found..

Table 5 :Procedural information

General information	Clinical information	Device performance
Date of Admission	Etiology	Valve size and serial number
Date of Procedure	Diagnosis for replacement	Post-operative TEE (within 1 hour)
Implanting Surgeon	Valve implant	REFER TO ECHO MANUAL
Type of Operation	Condition of the native aortic valve	
	Sizing	
	Concomitant procedures	
	Intraoperative Adverse Events	

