10.6 DEVICE REMOVAL / EXPLANT

Index valve 'removal' is the excision of the investigational valve, before implant of the investigational valve is complete, i.e., the heart is not restarted with the investigational valve in place. If the surgeon is unable to satisfactorily position or sew in the index valve, it will be removed and returned to the trial Sponsor who will provide a return valve kit. If the heart is restarted, the valve will be considered implanted and if removal is required from this point forward, it will be considered an explant.

In the event a valve is explanted, a copy of the procedure report must be provided to the trial Sponsor. Information on the cause of explant and its relationship to the valve will be provided by the investigator(s). Explanted valves must be returned to the trial Sponsor for analysis. Return kits for devices will be provided by the trial Sponsor.

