**** If Model 11000 is selected, please complete the following questions: ****

On what attempt was the study valve implanted?

- 1 *(If '1' is selected, please fill out one (1) Device Performance form)*
- 2 *(If '2' is selected, please fill out two (2) Device Performance forms)*

Was a post-implant echocardiogram performed? No Yes

Please complete the following questions:

Time echocardiogram started: (HH:MM)

What type of echocardiogram was done?

What was the severity of central regurgitation for the study valve?

What was the severity of paravalvular leak for the study valve?

Was observed regurgitation clinically acceptable? No Yes***** If Commercial Valve is selected, please complete the following questions: *****

After which study valve attempt was a commercial valve implanted?

- 1 *(If '1' is selected, please fill out one (1) Device Performance form (PERF).*

Why was a second attempt to implant the study valve not performed?

Please specify:

- 2 *(If '2' is selected, please fill out two (2) Device Performance forms (PERF).*

Please provide the following information about the commercial valve:

Manufacturer and Model:

Valve size: (mm)

Study

Doc#

Subject ID

Site

Visit Date

Status

Visit Name

Subevent#

CRF Name

Blank CRF

Did any adverse events occur during the surgery?

No

Yes If Yes, please ensure an adverse event form has been completed for each event.

Are the event(s) that occurred within the following AE classifications?

No Yes Blood and Lymphatic (Including ALL Bleeding complications)

No Yes Cardiovascular - Arrhythmia

No Yes Cardiovascular - Regurgitation

No Yes Cardiovascular - Stenosis

No Yes Cardiovascular - Embolic Event/Valve Thrombosis

No Yes Cardiovascular - Misc

No Yes Device Dysfunction

No Yes Gastrointestinal/Hepatic

No Yes Genitourinary/Renal

No Yes Pulmonary/Respiratory

No Yes Peripheral Vascular

No Yes Psychiatric

No Yes Muscular Skeletal/Dermatologic

No Yes Nonspecific or Unknown Body System

Study Doc#

Subject ID Site Visit Date Status

Visit Name Subevent# CRF Name Blank CRF

Was there a bleeding-related reoperation within the first 24 hours after surgery? No Yes

Please provide the times at which the following procedural steps were performed:

Start skin incision: (HH:MM)

Start ECC (Pump): (HH:MM)

Start cross clamp: (HH:MM)

Start sizing: (HH:MM)

Remove cross clamp: (HH:MM)

End ECC (Pump): (HH:MM)

End Skin closure: (HH:MM)

Comments

Study Doc#

Subject ID Site Visit Date Status

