Visit Name Subevent# CRF Name Blank CRF

DEVICE PERFORMANCE

Rev B

What study valve implant attempt was being performed?

Please provide the following information about the study valve:

Valve size:

Serial Number:

What type of sizer was used?

Please specify:

What was the barrel size of the valve sizer? mm

What suture technique was used to secure the valve?

Please specify:

How was the valve positioned?

Did the study valve perform as intended?

No

Please indicate the types of valve failures observed:

Failure type:

Please specify:

Failure type:

Please specify:

Failure type:

Please specify:

Failure type:

Please specify:

Yes

Study

Doc#

Subject ID

Site

Visit Date

Status

Visit Name

Subevent#

CRF Name

Blank CRF

DEVICE TECHNICAL SUCCESS:

Did the subject leave the operating room with the study valve in place for this attempt?

No

Why did the implant attempt fail?

Please specify:

Was the heart restarted after this implant attempt? No Yes

Yes

VALVE IMPLANT TIMES:

Start the study procedure (first stitch):

(HH:MM:SS)

Complete the study procedure (last stitch tied down on the valve):

(HH:MM:SS)

Comments

Subject ID

Site

Visit Date

Status

Visit Name

Subevent#

CRF Name

Blank CRF

DISCHARGE

Version A

Date of discharge (DD/MMM/YYYY)

Where was the subject discharged to?

Please provide the following information about the subject's hospitalization after the study valve procedure

Duration of time in the Intensive Care Unit (ICU)

Days and Hours

Duration of time in the Intermediate Care / High Dependency Unit

Days and Hours

Duration of time in the General Ward

Days and Hours

When was the transthoracic echocardiogram (TTE) performed?

Study

Doc#

Subject ID

Site

Visit Date

Status

Visit Name

Subevent#

CRF Name

Blank CRF

ADVERSE EVENT

Rev B

Event Onset Date

(DD/MMM/YYYY)

Site Awareness Date

(DD/MMM/YYYY)

Timing of Event Onset

Please select the AE Classification:

- Blood and Lymphatic (Including ALL Bleeding complications)

- Cardiovascular - Arrhythmia

- Cardiovascular - Regurgitation

- Cardiovascular - Stenosis

- Cardiovascular - Embolic Event/Valve Thrombosis

- Cardiovascular - Misc

- Device Dysfunction

- Gastrointestinal/Hepatic

- Genitourinary/Renal

- Pulmonary/Respiratory

- Peripheral Vascular

- Psychiatric

- Muscular Skeletal/ Dermatologic

- Nonspecific or Unknown Body System

Study Doc#

Subject ID Site Visit Date Status

Visit Name Subevent# CRF Name Blank CRF

Event Summary/Comments

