15.4 PROTOCOL DEVIATION CODES

PROTOCOL DEVIATION CODES

SUBJECT SCREENING

- 1.01 SUBJECT DID NOT MEET INCLUSION CRITERION
- 1.02 SUBJECT MET EXCLUSION CRITERION
- 1.03 DATE OF INFORMED CONSENT IS AFTER DATE OF STUDY ENROLLMENT
- 1.04 INFORMED CONSENT WAS IMPROPERLY OBTAINED
- 1.05 PERSON OBTAINING INFORMED CONSENT DID NOT SIGN/DATE THE CONSENT FORM
- 1.06 OTHER SCREENING DEVIATION

BASELINE

- 2.01 BASELINE ECHOCARDIOGRAM NOT DONE
- 2.02 BASELINE ECHOCARDIOGRAM DONE > 30 DAYS PRIOR IMPLANT DATE
- 2.03 BASELINE BLOOD NOT DONE
- 2.04 BASELINE BLOOD DONE > 30 DAYS BEFORE IMPLANT
- 2.05 BASELINE BLOOD INCOMPLETE
- 2.06 BASELINE COAGULATION PROFILE NOT DONE
- 2.07 BASELINE COAGULATION PROFILE DONE > 30 DAYS BEFORE IMPLANT
- 2.08 BASELINE NYHA NOT DONE
- 2.09 BASELINE ELECTROCARDIOGRAM NOT DONE
- 2.10 BASELINE ELECTROCARDIOGRAM DONE > 30 DAYS BEFORE IMPLANT
- 2.11 BASELINE EQ-5D NOT DONE
- 2.12 BASELINE SF-12 NOT DONE
- 2.12 BASELINE PHYSICAL ASSESSMENT / VITAL SIGNS NOT DONE
- 2.13 PREGNACY TEST NOT DONE
- 2.14 MEDICAL HISTORY NOT COLLECTED
- 2.15 OTHER BASELINE DEVIATION

IMPLANT SURGERY

- 3.01 IMPLANTING SURGEON IS NOT ON APPROVED LIST
- 3.02 PROCEDURE DIAGNOSIS NOT DONE
- 3.03 INCORRECT SIZER USED
- 3.04 SKIN INCISION TIME NOT RECORDED
- 3.05 START TIME OF ECC (PUMP) NOT RECORDED
- 3.06 START CROSS CLAMP TIME NOT RECORDED
- 3.07 START OF SIZING TIME NOT RECORDED
- 3.08 REMOVAL CROSS CLAMP TIME NOT RECORDED
- 3.09 END ECC (PUMP) TIME NOT RECORDED
- 3.10 SKIN CLOSURE TIME NOT RECORDED
- 3.11 UNAPPROVED CONCOMITANT PROCEDURE PERFORMED
- 3.12 VALVE SERIAL NUMBER NOT RECORDED

- 3.13 MORE THAN 2 STUDY VALVES ATTEMPTED TO BE IMPLANTED
- 3.14 TIME FIST STITCH PLACED ON THE VALVE NOT RECORDED
- 3.15 COMPLETION TIME OF STUDY PROCEDURE (LAST STITCH TIED DOWN ON THE VALVE) NOT RECORDED
- 3.16 POST-IMPLANT ECHOCARDIOGRAM NOT DONE
- 3.17 POST-IMPLANT ECHOCARDIOGRAM NOT DONE WITHIN 1 HOUR OF REMOVING THE CROSS-CLAMP
- 3.18 OTHER PROCEDURE DEVIATION

DISCHARGE

- 4.01 DISCHARGE OR 10-DAY ECHOCARDIOGRAM NOT DONE
- 4.02 DISCHARGE OR 10-DAY ECHOCARDIOGRAM DONE > 10 DAYS POST IMPLANT DATE
- 4.03 DISCHARGE PHYSICAL ASSESSMENT / VITAL SIGNS NOT DONE
- 4.04 DISCHARGE ELECTROCARDIOGRAM NOT DONE
- 4.05 DISCHARGE COAGULATION PROFILE NOT DONE
- 4.06 DISCHARGE MEDICATIONS NOT ASSESSED
- 4.07 OTHER DISCHARGE DEVIATION

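### Read together, 10.6 and 10.8 end follow-up of a subject whose first Model 11000 is replaced after heart restart by a second Model 11000, although a study valve is still in place

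*Combined protocol and SAP*

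**What the plan says.** **Removal versus explant (10.6).** The dividing line is heart restart. Excision is a removal only if "the heart is not restarted with the investigational valve in place". After restart, "the valve will be considered implanted and if removal is required from this point forward, it will be considered an explant". The section does not mention what replaces the valve.

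**Exit (10.8).** The list of exit reasons includes "Subject has trial device explanted". Its asterisk leads to a footnote, shared with subjects in whom the implant could not be completed, that sets follow-up at 30 days or until adverse events are resolved, and then exit.

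**Second attempts (15.3 and 15.4).** If Model 11000 was implanted, the Surgery Data form asks "On what attempt was the study valve implanted", with answers 1 and 2. The Device Performance form is completed for each attempt. If the subject did not leave the operating room with that attempt's valve, it asks "Was the heart restarted after this implant attempt". Deviation code 3.13 is "MORE THAN 2 STUDY VALVES ATTEMPTED TO BE IMPLANTED", so a second study valve is within plan.

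**Population and visits (9.2 and 10.4.3).** The performance population is "defined as all subjects that are enrolled into the trial and that are implanted with the index valve". Section 10.4.3 schedules visits from 3 months to 5 years for every enrolled subject.

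**The concern.** A subject can leave the operating room with a working Model 11000 and already meet an exit criterion, because an earlier Model 11000 was taken out after the heart had been restarted. If a site applies 10.8 as written, that subject leaves the trial before the first outpatient visit.

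The trial exists to describe the safety and performance of this valve, so carriers of the valve are the subjects it needs to follow. Those lost would not be a random subset, since they are subjects whose first implant did not work. Their exit removes late exposure from the linearized rates in 9.3 and ends their contribution to the Kaplan-Meier estimates for a reason related to valve fit. It also takes them out of the echo and NYHA summaries from 3 months onward and the 1-year quality-of-life summary. Two sites reading the same text could also handle the same case differently.

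**Working it through.** The plan has no figure to reproduce here. Section 9.1 gives only a maximum of 200 subjects, and no section states how often a second study valve is expected. The check is therefore a reading of the sections together, followed by simple arithmetic on exposure.

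**Step 1: follow one subject through the text.** Attempt 1 places a Model 11000 and the heart is restarted. The valve is then taken out and attempt 2 places another Model 11000.

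| Source | Status of this subject |
|---|---|
| 10.6 | First valve was implanted; taking it out is an explant |
| 10.8 | Trial device explanted, so exit at 30 days or on adverse-event resolution |
| 15.3 Surgery Data | Model 11000 implanted, attempt 2 |
| 15.3 Device Performance, attempt 1 | Valve did not leave the operating room; heart restarted: yes |
| 15.4 code 3.13 | No deviation (two valves, not more than two) |
| 9.2 | In the index valve population |
| 10.4.3 | Due for visits at 3 months and years 1 to 5 |

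Only 10.8 ends follow-up, and no section supplies an exception. The form questions show that both a second study valve and a failed attempt after restart were foreseen.

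**Step 2: what the earliest exit would remove.** Explant and implant fall on the same day, so the earliest exit is day 30.

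- Late period (9.3): more than 30 days after the procedure. Exit at day 30 gives 0 late-subject years.
- 3-month window (Table 7): plus or minus 1 month, so it opens at about 2 × 30.44 = 61 days, after the exit.
- Scheduled visits lost: 3 months and years 1, 2, 3, 4 and 5, which is 6.
- Unconditional transthoracic echoes lost (Table 3): 3 months and years 1, 3 and 5, which is 4. Those at years 2 and 4 depend on a murmur.

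**Step 3: late exposure.**

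- Per full-term subject: (5 × 365.25 − 30) / 365.25 = 4.918 years.
- Ceiling for the trial: 200 × 4.918 = 983.6 years, if 200 are enrolled and all complete 5 years.
- One subject's share: 4.918 / 983.6 = 0.5%.

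The number of affected subjects is an assumption, shown as a range:

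| Subjects exited at day 30 | Late-subject years lost | Share of ceiling |
|---|---|---|
| 1 | 4.9 | 0.5% |
| 2 | 9.8 | 1.0% |
| 5 | 24.6 | 2.5% |
| 10 | 49.2 | 5.0% |

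**The case against.** The strongest reply is that 10.8 does not mean this. It opens by tying exit to nothing further being due from the subject, whereas 10.4.3 still has visits due. The explant line shares its footnote only with subjects in whom the implant could not be completed, and the footnote treats the two as one cohort. That reads as subjects left without a study valve. The forms also record the attempt-2 recipient as implanted with a Model 11000. This is good evidence of intent, and it stands as such. It does not supply the missing exception, because a site coordinator or programmer who applies the written line would exit the subject.

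The exclusion for prior implantation of the trial device does not settle it either. That is an entry criterion, and its footnote sets completion at heart restart plus coming off bypass, whereas 10.6 uses restart alone.

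A second reply concerns size. The scenario is rare, its frequency is assumed, every safety endpoint is descriptive, and no hypothesis or performance goal depends on it. All of that is fair and limits the weight of the point.

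A reader might also infer a mirror-image error: that a subject converted to a commercial valve after restart counts as implanted under 10.6, so that the other valve's discharge echo enters the Model 11000 tables in 9.4. The documents do not support this as a finding. The Surgery Data form makes Model 11000 and commercial valve alternative answers to one question and records the commercial valve's manufacturer, model and size separately, so such a subject is readily kept out of the index valve population.

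**Conclusion.** The conflict is real on the text: 10.6 and 10.8 together exit a subject who still carries a Model 11000, against 9.2 and 10.4.3. It is most likely a drafting gap rather than a decision to stop following such subjects.

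The size is small and depends on an unknown count. Each affected subject could lose up to 4.9 late-subject years, 0.5% of the 984-year ceiling. Real exposure will fall below that ceiling through death, withdrawal and loss to follow-up. What makes the loss worth preventing is its selection for difficult first implants.

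Three stronger readings should be avoided:

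- **That every such subject leaves at day 30 and adds nothing to the late rates.** Day 30 is only the earliest exit. The footnote also allows follow-up until adverse events resolve, which may be later in these subjects.
- **That a particular percentage of subjects will be affected.** The documents give no frequency.
- **That replacements prompted by the post-implant transesophageal echo usually follow heart restart.** Section 10.2.3 times that echo from cross-clamp removal, which makes the sequence plausible, but the documents do not state it. The point does not need it, since the Device Performance form already foresees a failed attempt after restart.

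**What to change.** Reconcile 10.8 with 10.6, 9.2 and 10.4.3 by limiting the exit line to: *trial device explanted and no Model 11000 left in place*. Add that a subject who leaves the index operation with a Model 11000, on attempt 1 or 2, stays in scheduled follow-up. State also that the first valve's removal after restart still counts as an early event for the Explant endpoint in 7.3.1, so that the change does not hide a device failure.

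As a minor consistency point, 9.2 or 9.4 can say that hemodynamic summaries use echoes of a Model 11000 in situ, identified by the existing Surgery Data item on which valve was implanted.

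The cost is one line in 10.8 and, optionally, one in 9.2 or 9.4. No new data field is needed, because the Surgery Data and Device Performance forms already identify these subjects. The only added burden is the ordinary visit schedule for the few subjects concerned. The change affects follow-up and analysis only, not surgical decisions.

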7.3 ENDPOINTS

7.3.1 SAFETY ENDPOINTS

Descriptive information of early rates and late linearized rates of the following:

- Structural valve deterioration
- Thromboembolism
- All bleeding/hemorrhage
- Major bleeding/hemorrhage
- All paravalvular leak
- Major paravalvular leak
- Non-structural valve dysfunction
- Endocarditis
- Hemolysis
- All cause mortality
- Trial valve-related mortality
- Explant

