9.3 SAFETY ANALYSIS

Early adverse events within 30 days of procedure will be reported as the number of events divided by the number of enrolled subjects. Linearized rates will be used to summarize adverse events for the late (>30 days) post-operative period. The linearized rates will be calculated as the number of late events divided by the total number of late-subject years.

Percentages for the early events and linearized rates for the late events also will be calculated for all other complications observed in the trial.

Actuarial rates based on the method of Kaplan-Meier will be calculated for each of the safety endpoints at each of the follow-up time points.

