10.4.3 FOLLOW-UP ASSESSMENTS

Post-procedure clinical evaluation will be performed on all enrolled trial subjects at scheduled visits at the trial site. The follow-up windows are listed in **Table 7**.

Table 7: Follow-up Windows

Follow-up Assessment*	Assessment Window
3 months	± 1 month
1 year	± 1 month
2 years	± 3 month
3 years	± 3 month
4 years	± 3 month
5 years	± 3 month

*Follow-up visits are calculated from the implant date.

During each postoperative follow-up visit, the investigator(s) will determine the subject's availability for future follow-up visits. If any subject needs to be seen, at a time other than a regularly scheduled follow-up visit, due to an index device related event, the required data collection would be the same as the 1 year follow-up evaluation.

Table 8 Follow-Up Information at all Post-Discharge Visits (3 months and annually to 5 years)

Clinical/Physical Assessment	Blood Studies	Echocardiography (TTE) ³
Date of Discharge	Blood Draw Date	Years 1, 3, 5:
Physical Assessment	White Blood Cell Count	Date of exam
Cardiac Rhythm (12-lead ECG)	Red Blood Cell Count	SEE ECHO MANUAL
NYHA Classification	Hemoglobin	Years 2, 4:
Quality of Life (EQ-5D & SF12-v2) ¹	Hematocrit	Date of exam
Anti-thromboembolic Therapy (medications)	Platelet Count	Auscultation ⁴
Adverse Events	Plasma Free Hemoglobin	
	Coagulation Profile ²	

¹ Quality of Life (EQ-5D and SF12-v2) will be completed only at the 1-year follow-up visit

² Coagulation profile will be completed only at years 1, 3, and 5

³ Exam to be performed as described in the Echo Manual. Data evaluation performed by a Core Lab.

⁴ TE will be the standard echo assessment for the aortic valve but will only be completed if murmur is heard on auscultation at year 2 and year 4 interval visits.

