10.7 MISSED SUBJECT VISITS

The Investigator(s) will make every attempt to follow the subjects and subjects will be encouraged by the Investigator(s) to report any address or telephone number changes to the trial site. They will also be informed of the importance of returning for scheduled follow-up visits even if they are not having any problems.

If a subject cannot be reached for a follow-up visit, the Investigator will document on the CRF, the efforts undertaken to contact the subject or the subject's primary health care provider. These efforts should include 2 attempts of telephone contact at separate dates and times, and a registered letter before the end of the follow-up window. If a subject cannot be reached for a follow-up visit, or misses a scheduled visit, the visit will be recorded as a missed visit on the date of last attempted contact. Subjects who miss a visit will not be considered withdrawn. At the next visit interval, the Investigator and/or designee will attempt to contact the subject again for follow-up. Should this attempt to contact the subject fail, a family member should be contacted in addition to the subject. Subjects who miss 2 sequential follow-up visits will be considered lost to follow-up at the second missed visit and exempt from further trial follow-up. After the subject is terminated from the trial, the Investigator will attempt to determine if the subject is alive, including searching national mortality registries as permitted by local laws.

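### Early exit after explant or failed implant (Section 10.8) would in effect censor all-cause mortality at a possibly informative time, and no rule extends the vital-status check to these subjects

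*Combined protocol and SAP*

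**What the plan says.** Section 10.3 sets enrollment in the operating room, when the surgeon attempts the implant. A subject whose implant then fails is therefore enrolled. Section 9.2 states: "The analyses of safety data will include all enrolled subjects". Section 7.3.1 introduces its list of safety endpoints, which includes all-cause mortality, as "Descriptive information of early rates and late linearized rates of the following". Section 9.3 adds: "Actuarial rates based on the method of Kaplan-Meier will be calculated for each of the safety endpoints", at each follow-up time point. Table 7 in Section 10.4.3 carries those time points to 5 years. Section 9.6 rules out imputation.

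Section 10.8 lists the reasons for exit. Two carry a footnote: an enrolled subject whose implant could not be completed, and a subject whose trial device is explanted. The footnote reads: "Subjects will be followed for 30 days or until any adverse events experienced by this cohort are resolved and then will be exited". The same section describes exit in these words: "Trial Subjects exit the trial when no additional follow-up visits, procedures, or data collection are required".

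Two other passages bear on this. Section 10.4.3 says: "Post-procedure clinical evaluation will be performed on all enrolled trial subjects at scheduled visits at the trial site". Section 10.7 says: "Subjects who miss 2 sequential follow-up visits will be considered lost to follow-up at the second missed visit", and then: "After the subject is terminated from the trial, the Investigator will attempt to determine if the subject is alive". The latter includes a search of national mortality registries where local law allows.

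**The concern.** All-cause mortality needs neither the trial valve in place nor a clinic visit, so nothing about the endpoint requires follow-up to end at explant or failed implant. Read together, the rules keep these subjects in the denominator population but stop looking for their deaths soon after the event. Kaplan-Meier estimation assumes that subjects who leave observation have the same later risk of death as those who stay. An exit triggered by explant or by a failed implant may break that assumption.

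At stake is the 5-year all-cause mortality figure, together with the late linearized rate, which loses both the later deaths and the later subject-years. The figure would be too low if risk after these exits is higher than in other subjects, slightly too high if it is lower, and unbiased if it is equal. Endpoints that depend on the valve, such as structural deterioration or paravalvular leak, are not at issue: stopping those at explant is sensible.

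**Working it through.** The plan states no rates, margin or precision, so it has no figure of its own to reproduce. The calculation below shows size only.

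**From the documents:** at most 200 subjects (9.1); follow-up to 5 years; late period after day 30 (9.3); exit 30 days after the event, ignoring the alternative of adverse-event resolution.

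**Assumed:** late death hazard h = 0.03 per year; explant rate e = 0.5% or 1% per year; failed-implant share f = 1%, 2% or 5%; death hazard after the event r = 0.5, 1, 2 or 4 times that of other subjects.

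**Step 1, late period.** 5 − 30/365.25 = 4.918 years. Mortality among subjects without an event: 1 − exp(−0.03 × 4.918) = 13.72%.

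**Step 2, failed implants.** Exit at day 30 removes all their late follow-up, so the reported figure is 13.72%. The complete figure is (1 − f)(1 − exp(−h × 4.918)) + f(1 − exp(−r × h × 4.918)). For f = 0.02 and r = 4 this is 0.98 × 0.1372 + 0.02 × 0.4458 = 14.33%, a shift of −0.62 points before rounding.

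**Step 3, explants.** The expected number is 200 × e/(e + h) × (1 − exp(−(e + h) × 4.918)), which gives 4.5 at 0.5% per year and 8.9 at 1%. The period was divided into small time steps. The Kaplan-Meier hazard at each step is deaths under observation over subjects under observation, with explanted subjects leaving observation after 30 days. The complete figure counts all deaths.

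**Step 4, shifts** (reported minus complete 5-year mortality, percentage points):

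| Assumption | Subjects affected | r = 0.5 | r = 1 | r = 2 | r = 4 |
|---|---|---|---|---|---|
| Explant 0.5%/yr | 4.5 | +0.08 | 0 | −0.14 | −0.39 |
| Explant 1%/yr | 8.9 | +0.15 | 0 | −0.28 | −0.77 |
| Failed implant 1% | 2 | +0.07 | 0 | −0.12 | −0.31 |
| Failed implant 2% | 4 | +0.13 | 0 | −0.24 | −0.62 |
| Failed implant 5% | 10 | +0.33 | 0 | −0.59 | −1.54 |
| Explant 0.5%/yr and failed implant 2% | about 8.4 | +0.21 | 0 | −0.38 | −1.00 |

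**Step 5, yardstick.** The standard error of a 13.72% rate with 200 subjects is √(0.1372 × 0.8628/200) = 2.4 points.

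**Step 6, wider assumptions.** The grid was failed implants 0 or 2%, explants 0.3, 1 or 2% per year, deaths 2 or 4% per year, and r = 1, 2 or 4, giving 36 combinations. Understatement is 0 at r = 1, 0.06 to 0.99 points at r = 2, and 0.18 to 2.56 points at r = 4. Seven combinations exceed 1 point, all at r = 4. The largest has a Kaplan-Meier estimate of 18.22%, for which the standard error is √(0.1822 × 0.8178/200) = 2.7 points.

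**Limit of the model.** It exits everyone at exactly 30 days. Section 11.1 has adverse events followed until resolved or explained, which points to the later of the two times in the footnote. Deaths arising from unresolved events would then be captured before exit, so the larger figures probably overstate the effect.

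**The case against.** The strongest reply is that Section 10.7 already provides the remedy. Its sentence on establishing whether a subject is alive is not limited by its own words to subjects lost to follow-up. Loss to follow-up is itself on the Section 10.8 exit list, so the plan plainly allows vital status to be sought after exit. That much stands, and it shows that such ascertainment is feasible. But the sentence sits under missed visits, directly after the lost-to-follow-up rule. It sets no time horizon, is not linked to the Section 10.8 footnote, and is not used by any rule in Section 9. It does not clearly cover these exits.

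It can also be said that the trial concerns Model 11000, that later deaths occur without that valve, and that valve-related mortality is a separate endpoint. This supports stopping valve-dependent endpoints. It does not support stopping all-cause mortality, which Section 9.2 assigns to all enrolled subjects. The surgery form provides for a commercial valve after a failed attempt, so a hazard ratio near 1 is plausible for that group, and the bias there may be nil.

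The conflict with Section 10.4.3 is softer than it looks: its visits are counted from the implant date, which a failed implant lacks, and Section 10.8 is the more specific rule. The wording still needs reconciling.

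Two stronger readings are tempting. A reader might infer that the plan prescribes censoring, or forbids data after exit. It does neither: Section 9 has no censoring rule, and Section 10.8 says when exit occurs. A reader might also infer that censoring is tied to valve failure. Section 10.8 exits any explant whatever its cause, and Section 10.6 asks for that cause separately.

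**Conclusion.** The concern holds as a minor point. Following the written rules, deaths after explant or failed implant, once the subject has exited, would be missing from an endpoint defined on all enrolled subjects. The censoring is an inference from early exit, Kaplan-Meier estimation and no imputation; the plan does not state it.

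The size rests wholly on assumed rates. The shift is zero at equal risk and mostly within about 1 point otherwise. It passes 1 point only with a fourfold later risk of death combined with the higher event or death rates, and it stays inside the sampling error. A reader might infer that reported mortality will be materially understated. The documents do not support that: they give no explant, failed-implant or mortality rates, the direction depends on the later risk, and Section 9 has no test or performance criterion that such a shift could change. The case for acting is that the gap is linked to the course of treatment, is hard to repair afterwards, and costs little to close.

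How data after a valve-in-valve procedure are handled is a separate clarification and not part of this conclusion.

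**What to change.** - **Section 10.7:** state that the vital-status check (telephone or registry, as consent and local law permit) runs to 5 years from the procedure for all enrolled subjects who have not withdrawn consent, including after explant or failed implant.
- **Section 9.3:** state that all-cause mortality is not censored at those exits, while valve-dependent endpoints may stop at explant.
- **Section 10.8:** reconcile the exit wording with Sections 10.4.3 and 11.1, including whether the earlier or the later of the two times in the footnote applies.

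The cost is a few sentences and a few vital-status checks a year. Consent cover must be confirmed: Section 7 gives a 5-year consent period but not its scope, and the text of the sample consent form was not available for this review. The reported mortality may come out slightly less favourable.
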